17. REDUNDANCY

To minimize risks to subjects, whenever appropriate, use procedures already being performed on the subjects for diagnostic or treatment purposes. Describe provisions.

N/A

18. COUNSELING

In projects dealing with sensitive topics (e.g., depression, abortion, intimate relationships, etc.) appropriate follow-up counseling services must be made available to which subjects might be referred.

The IRB should be notified of these services and how they will be made available to subjects.

Although we do not foresee any Serious Adverse Events (SAE) or Adverse Events (AE) as a result of participating in this study, PI [name] will personally offer a brief one-time in-person or phone counseling and assessment session to all student participants reporting alcohol, drug, and mental health related Adverse Events (AEs) and Serious Adverse Events (SAEs) regardless of their relation

to the intervention study in order to assess the situation and offer referral resources. If an AE or SAE occurs, PI [name] will first refer the student will be referred to the Community of Care. He will also provide participants with referrals to appropriate personnel at LMU's Student Psychological Services (SPS), the Student Health Center (SHC), and/or outside non-LMU resources. If a SAE is life-threatening, [name] will contact public safety if required. Should there be any unanticipated problems that detract from a positive parent or student participant experience in the study, issues will be addressed with participants immediately, and PI [name] will work with the University's IRB to swiftly develop and enact a resolution plan. All SAEs, AEs and unanticipated problems will be managed consistent with University IRB guidelines. Additionally, any SAEs or AEs will be reported to the NIH/NIAAA within 24 hours.

If data reveals a SAE or we learn of it through a student, their PIN number associated with their survey data will be located. We will then search the separate data file for the student's contact information. Listed below are the specific resources which will be provided to students if an SAE or AE occurs.

LMU Resources:

[name]: [contact]; [contact]

Community of Care: [contact]

SPS: [contact]

SHS: [contact];

<https://studentaffairs.lmu.edu/wellness/studenthealthservices/scheduleanappointment/>

Non-LMU Resources:

Drug Addiction & Alcohol Abuse Help & Information Resources: <https://www.addict-help.com/>

NIAAA Alcohol Treatment Navigator: <https://alcoholtreatment.niaaa.nih.gov/>

Substance Abuse and Mental Health Services Administration:

<https://www.samhsa.gov/>

19. SAFEGUARDING IDENTITY

When a research project involves the study of behaviors that are considered criminal or socially deviant (i.e., alcohol or drug use) special care should be taken to protect the identities of participating subjects.

In certain instances, principal investigators may apply for "Confidentiality Certificates" from the Department of Health and Human Services or for "Grants of Confidentiality" from the Department of Justice.

Please see response to question 5. Numerous safeguards will be put in place to protect participant's identities.

20. ADVERTISEMENTS

If advertisements for subjects are to be used, attach a copy and identify the medium of display.

N/A

21. FOREIGN RESEARCH

When research takes place in a foreign culture, the investigator must consider the ethical principles of that culture in addition to the principles listed above.

N/A

22. EXEMPTION CATEGORIES (45 CFR 46.101(b) 1-6)

If you believe your study falls into any of the Exemption Categories listed below, please explain which category(ies) you believe it falls into and why.

- 1) Research conducted in established or commonly accepted educational settings, involving normal educational practices, such as (i) research on regular and special instructional strategies, or (ii) research on the effectiveness of or the comparison among instructional techniques, curricula, or classroom management methods.
- 2) Research involving the use of educational tests (cognitive, diagnostic, aptitude, achievement), if information taken from these sources is recorded in such a manner that subjects cannot be identified, directly or through identifiers linked to the subjects.
- 3) Research involving survey or interview procedures, except where all of the following conditions exist: (i) responses are recorded in such a manner that the human subjects can be identified, directly or through identifiers linked to the subjects, (ii) the subject's responses, if they became known outside the research, could reasonably place the subject at risk of criminal or civil liability, or be damaging to the subject's financial standing, employability, or reputation, and (iii) the research deals with sensitive aspects of the subject's own behavior, such as illegal conduct, drug use, sexual behavior, or use of alcohol.

All research involving survey or interview procedures is exempt, without exception, when the respondents are elected or appointed public officials, or candidates for public office.

- 4) Research involving the observation (including observation by participants) of public behavior, except where all of the following conditions exist: (i) observations are recorded in such a manner that the human subjects can be identified, directly or through the identifiers linked to the subjects, (ii) the observations recorded about the individual, if they became known outside the research, could reasonably place the subject at risk of criminal or civil liability, or be damaging to the subject's financial standing, employability, or reputation, and (iii) the research deals with sensitive aspects of the subject's own behavior such as illegal conduct, drug use, sexual behavior, or use of alcohol.
- 5) Research involving the collection or study of existing data, documents, records, pathological specimens, or diagnostic specimens, if these sources are publicly available or if the information is recorded by the investigator in such a manner that subjects cannot be identified, directly or through identifiers linked to the subjects.
- 6) Unless specifically required by statute (and except to the extent specified in paragraph (1)), research and demonstration projects which are conducted by or subject to the approval of the Department of Health and Human Services, and which are designed to study, evaluate, or otherwise examine: (i) programs under the Social Security Act or other public benefit or service programs, (ii) procedures for obtaining benefits or services under those programs, (iii) possible changes in or alternatives to those programs or procedures, or (iv) possible changes in methods or levels of payment for benefits or services under those programs.

N/A

Please deliver to: [name], IRB Coordinator, [name] or [contact].

MEASURES APPENDIX

I was born...

- Female (0)
- Male (1)

I identify as...

- Female (0)
- Male (1)
- Other (2)

I am...

- Heterosexual/Straight (1)
- Gay/Lesbian (2)
- Bisexual (3)
- Queer (4)
- I'm not sure (5)

I consider myself...

- American Indian or Alaska Native (1)
- Asian (2)
- Black or African American (3)
- Native Hawaiian or Other Pacific Islander (4)
- White (5)
- Multiracial (6)

Ethnically, I am...

- Hispanic/Latino (1)
- Not Hispanic/Latino (0)

My age is...

- Under 17 (0)
- 17 (1)
- 18 (2)
- 19 (3)
- 20 (4)
- 21 or over (5)

What is your height?

Feet:

▼ 3 (3) ... 8 (8)

Inches:

▼ 0 (0) ... 11 (11)

What is your weight in pounds?

Are your parents...

- Married (1)
- Divorced (2)
- Separated (3)
- Other (please explain): (4)

Were you living with your parents during your senior year of high school?

- Yes (1)
- No (0)

Who were you living with most of the time during your senior year of high school?

- Mother (1)
- Father (2)
- Other (please explain): (3)

Where are you **currently** living?

- With my parent(s) (1)
- In the LMU dorms (2)
- Off campus with roommates (3)
- Off campus alone (4)
- Other (5)

How often do you see or communicate with your **father** in person or online?

- Never (0)
- Less than monthly basis (1)
- Monthly basis (2)
- Weekly basis (3)
- Daily basis (4)

How often do you see or communicate with your **mother** in person or online?

- Never (0)
- Less than monthly basis (1)
- Monthly basis (2)
- Weekly basis (3)
- Daily basis (4)

The next set of questions will ask about your drinking habits. You may not know the exact answer to all of these questions; in those cases, please make your best guess. Please keep in mind that your responses to the questions in this survey are confidential.

How old were you when you had your first drink of alcohol (more than a sip or a taste)?

▼ I have never tried alcohol (0) ... 21 or older (10)

Who gave you your first drink of alcohol (more than just a sip or taste)?

- Parent (1)
- Family member (not a parent) (2)
- Friend (3)
- Stranger (4)
- I have never tried alcohol (0)

Which best describes your alcohol use?

- I have never tried alcohol (0)
- I am an abstainer (I do not drink at all, but have tried before) (1)
- I am a light drinker (2)
- I am a moderate drinker (3)
- I am a heavy drinker (4)
- I am a problem drinker (5)

This section asks you to report on your drinking over the **past 30 days**.

For all questions, **one drink equals**:

Consider a typical week during the past 30 days. How much alcohol, on average (measured in number of drinks), do you drink on each day of a typical week? If your answer is zero, please enter 0.

	Monday (1)	Tuesday (2)	Wednesday (3)	Thursday (4)	Friday (5)	Saturday (6)	Sunday (7)
Number of drinks							

During the **past 30 days**, on average, how many days per week did you drink?

▼ 0 (1) ... 7 (7)

During the **past 30 days**, on average, how many drinks did you have each time you drank?

▼ 0 (0) ... 25+ (25)

During the **past 30 days**, what is the **maximum** number of drinks you drank during any one drinking occasion?

▼ 0 (0) ... 25+ (25)

Think of the occasion you drank the most in the **past 30 days**. How many **hours** did you spend drinking on that occasion?

During the **past 30 days**, how many times did you have [four/give] or more drinks within a 2 hour period?

▼ 0 occasions (0) ... 7+ occasions (7)

During the **past 30 days**, how many times did you have [eight/ten] or more drinks within a 2 hour period?

▼ 0 occasions (0) ... 7+ occasions (7)

Note: The BYAACQ was used in place of the RAPI to measure alcohol consequences.

Below is a list of things that sometimes happen to people either during or after they have been drinking alcohol. Next to each item below, please indicate whether that item describes something that has happened to you in the **past 30 days**.

PRS Cover Page for Statistical Analysis Plan

Title: Parent Feedback Intervention Targeting Student Transitions and Alcohol Related Trajectories (+) Efficacy Study (FITSTART+)

Date: April 26, 2021

ClinicalTrials.gov Identifier: NCT04549454

Statistical Analysis Plan

Examines the efficacy of FITSTART+. Main effects of the intervention will be examined with hierarchical generalized linear models (HGLM) using SAS. HGLM permits the simultaneous examination of relationships among variables at different levels, for example variables measured over assessment periods assumed to fluctuate within an individual (e.g., student drinking behavior) with variables considered to have stable characteristics (i.e., parent intervention condition). Using this framework, time will be specified as a Level 1 varying predictor nested within individuals (Level 2). The following model will be used to determine main effects of the intervention conditions compared to control:

$$\text{Level 1: } DV_{ti} = \pi_{0i} + \pi_{1i}(T1)_{ti} + \pi_{2i}(T2)_{ti} + \varepsilon_{ti}$$

$$\text{Level 2: } \pi_{0i} = \beta_{00} + \beta_{01}(Tx)_i + r_{00i}$$

$$\pi_{1i} = \beta_{10} + \beta_{11}(Tx) \quad t \text{ indexes repeated measure} \quad \pi_{2i} = \beta_{20} + \beta_{21}(Tx) \quad i \text{ indexes individuals}$$

Respective model DVs will include total drinks per week from the DDQ, consequence composite score, and number of HED episodes during the past month. T1 and T2 will be dummy coded time variables (T1 = student baseline [coded 0] to 1 month into college follow-up [coded 1], T2 = student baseline [coded 0] to 6 months into college follow-up [coded 1]). Tx will be a categorical predictor comparing the intervention condition [coded 1] to control [coded 0]. With this model, intercept treatment differences will represent treatment differences at baseline (e.g., group differences in student drinking at baseline) and slope differences will represent changes over time (e.g., did students of intervention parents reduce their drinking between baseline and follow-up assessments more than students of control parents?). The intercept includes a random effect, which will model the subject-specific heterogeneity in the outcome and control for correlated data due to individuals. Pairwise comparisons (post hoc Tukey's) were conducted to examine mean differences between conditions at each time point.

Missing data. Attrition bias will be tested by evaluating whether baseline outcomes differ between student and parent dropouts versus completers. HGLM is optimal in that it allows for unbalanced data, giving heavier weights to participants with more non-missing values. HGLM also assumes that missing values are missing at random as opposed to non-ignorable. The pattern-mixture approach to non-ignorable missing data will be used to assess the sensitivity of findings to the presence of missing data. If the pattern of missingness appears to pose a threat to the validity of the experimental manipulation (i.e., student attrition is related to parent random assignment, or the predictors of attrition are different for students of intervention vs control parents), more powerful missing techniques will be used, such as multiple imputation.

Additional Model Considerations. Student outcomes (drinks per week, HED frequency, and negative consequences) are count variables, which can have skewed distributions when the overall mean is low. Alternative models could also specify a Poisson or Gaussian distribution for the Level 1 errors. We will consider whether the

Level 1 components are more appropriately modeled as Gaussian or Poisson. Further, in spite of randomization at the parent level, we will conduct baseline equivalence tests between the FITSTART+ student participants to establish successful parent randomization effectiveness, including pre-treatment alcohol use, negative consequences, and demographic variables. Any student variables that are associated with treatment assignment, in spite of parent randomization, will be included as covariates.

Power. *We have more conservatively aimed for sufficient statistical power to detect small effects on our primary student drinking outcomes (i.e., HED frequency, drinks per week, negative consequences).* Very low student attrition (13%) was achieved in the original FITSTART study across 10 months and three assessments. As identical procedures and similar assessments will be used in the current study, we expect to retain over 85% of students. Power analyses were calculated using the Optimal Design program for longitudinal HLM specifying two-study conditions and randomization at the person-level. Power curves with 20% attrition were plotted for sample size per treatment arm at two effect sizes: $d=.20$ (small effect) and $d=.40$ (medium effect). A sample size of 300 per arm was found to yield excellent power for detecting both effect sizes.

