All parents of students who complete the baseline survey will be invited via email to take part in the FITSTART+ program. To sign up, parents will need to click a link in the email to visit the FITSTART+ landing page which will include a general description of the application (no information about alcohol), a description of the parenting experts featured in the application, and a parent verification form. The verification form, which will be a Qualtrics survey embedded in the landing page, will serve two important purposes: it will (1) match parents to their students in the dataset; and (2) randomize parents to the treatment or control version of the app. The randomizer will be set up in Qualtrics to balance assignment to an app condition by students' birth sex. At the end of the verification form, parents will receive a web URL linking to the sign-up page for the application to which they were randomized. Parents who click the link will be prompted to create their user account. In order to not artificially bias parents' app use, parents will be unaware that there is more than one version of the app, they will not be incentivized to use the app, and they will not be told that their child is participating in a survey study.

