5. CONFIDENTIALITY

Will subjects be identifiable by name or other means? If subjects will be identifiable, explain the procedures that will be used for collecting, processing, and storing data. Who will have access to data? What will be done with the data when the study is completed? If you are collecting visual images of your subjects please justify this.

Parent/student dyads will be set up in order to link the data. To do this the parents and the students will share the same PIN. If more than one parent decides to participate their PINs will end in either -1 or -2. The sharing of PINs allows for the linkage of data without individuating information attached. This linkage is solely for analytic purposes and will only be used to look at student outcome data.

To maintain confidentiality of data submitted over the internet, participants will submit all information via Qualtrics (Qualtrics has SAS 70 Certification and meets the rigorous privacy standards imposed on health care records by the Health Insurance Portability and

Accountability Act). All Qualtrics accounts are hidden behind passwords and all data is protected with real-time data replication. Data transfer will be protected using a Secure Socket Layer with 128-bit encryption. This is the same level of encryption used for most banking transactions and offers the highest degree of protection available for data transfer. The server is physically located in a secure, commercially protected co-location facility with 24-hour locked and monitored keycard access, within a locked room, within a locked server rack, with a locking face-plate protecting the server itself from physical access without authorization. Electronic protection is provided by a commercial-grade firewall, with continuous monitoring of the server for any attempts at electronic invasion. Any associated paper documents will be stored in a locked file cabinet within the lab. Study results will be reported in aggregate, so that individual participants will not be identifiable in any research reports or presentations of the proposed study. As we often receive requests for our data to be used in meta-analyses, data from the study will be kept for 5 years after the completion of the project. After this period of time all data will be destroyed.

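### Baseline is measured before randomization, yet the main model leaves the baseline arm difference free; using the known equality would be a cheap gain in precision for small effects

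*SAP*

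**What the plan says.** The SAP model has three rows per student (baseline, 1 month, 6 months), two time indicators, a random intercept, and Tx in all three Level 2 equations. On the Tx term in the intercept it says: "With this model, intercept treatment differences will represent treatment differences at baseline". The treatment effects are the two Tx-by-time coefficients, that is, differences in change from baseline. Pairwise Tukey comparisons are a second contrast; they "were conducted to examine mean differences between conditions at each time point".

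The only covariate adjustment depends on baseline equivalence tests (SAP, Additional Model Considerations): "Any student variables that are associated with treatment assignment, in spite of parent randomization, will be included as covariates". The same paragraph leaves the error distribution open: "Alternative models could also specify a Poisson or Gaussian distribution for the Level 1 errors". The Power paragraph sets the target: "We have more conservatively aimed for sufficient statistical power to detect small effects on our primary student drinking outcomes".

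The order of events is in Protocol section 3: "All parents of students who complete the baseline survey will be invited via email to take part in the FITSTART+ program". Parents are randomized later, in the verification form on the landing page. Section 12 adds that the randomizer balances by the student's birth sex.

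**The concern.** Because baseline precedes randomization, any arm difference at baseline is due to chance. A model with a free baseline difference spends information estimating a quantity whose expected value is known to be zero. The Tx-by-time estimate then carries the full noise of the baseline difference. The per-visit comparison makes the opposite choice: with complete data it is the raw follow-up difference and makes no use of baseline.

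At stake is power for small effects, which is what the SAP says it is aiming at. Protocol section 2 also allows as few as 400 students in total.

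**Working it through.** **Plan's own figure.** The SAP calls power at 300 per arm excellent but gives no number, alpha, between-wave correlation or definition of d. There is nothing to reproduce, and what follows is not a re-check of that claim.

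**Inputs.** From the SAP: three waves, random intercept, 300 per arm, 20% attrition, d=.20 and d=.40. From Protocol section 2: 400 students as the lower limit, so 200 per arm. Assumed: Gaussian outcome with total variance 1; d is the 6-month arm difference in total SDs; between-wave correlation r = .3, .5, .7; dropout of 10% by 1 month and 20% by 6 months; two-sided 5%.

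**Complete data, n per arm.** Variances of the 6-month effect:

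- Tx-by-time, free baseline: (2/n) × 2(1 − r)
- Per-visit comparison: 2/n
- Common baseline mean: (2/n) × (1 − r²)

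The common-baseline variance is (1 + r)/2 of the Tx-by-time variance, a reduction of 35%, 25%, 15%. It is 1 − r² of the per-visit variance, a reduction of 9%, 25%, 49%. For n = 300 and r = .5 the standard errors are √(2/300 × 1) = .0816, √(2/300) = .0816 and √(2/300 × .75) = .0707.

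**With 20% dropout.** Generalized least squares for the SAP model, with and without Tx in the intercept, 300 per arm, 6 months. Power is Φ(d/SE − 1.96).

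| | r=.3 | r=.5 | r=.7 |
|---|---|---|---|
| SE, Tx-by-time as planned | .1039 | .0885 | .0691 |
| SE, per-visit as planned | .0902 | .0885 | .0862 |
| SE, common baseline | .0868 | .0786 | .0646 |
| Tx-by-time variance reduction | 30% | 21% | 13% |
| Power d=.20, Tx-by-time | 48.6% | 61.8% | 82.5% |
| Power d=.20, per-visit | 60.1% | 61.8% | 64.0% |
| Power d=.20, common baseline | 63.4% | 72.1% | 87.2% |

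Example, r = .3: .20/.1039 = 1.925 gives 48.6%; .20/.0868 = 2.304 gives 63.4%.

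Gain over the better planned contrast: 63.4 − 60.1 = 3.3; 72.1 − 61.8 = 10.3; 87.2 − 82.5 = 4.7 points.

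At 200 per arm and d=.20, Tx-by-time against common baseline is 34.9% vs 46.9%, 45.4% vs 54.7%, 65.7% vs 71.5%. At d=.40 and 300 per arm it is 97.0% vs 99.6%, 99.5% vs 99.9%, and over 99.9% for both.

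**Poisson.** Removing Tx from the intercept saved between 2% and 45% of the Tx-by-time variance over 15 assumed scenarios. The saving was smallest at high means with a large random-intercept variance and largest at low means with a small one.

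**Does the constraint preserve type I error?** Model-based against true variance, random intercept only, 240 per arm (300 less 20%), complete data, 6-month test. Correlations are baseline–1 month, baseline–6 months, 1–6 months; all values are assumed.

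| Correlations | SDs by wave | As planned | Common baseline |
|---|---|---|---|
| .5/.45/.65 | 1/1/1 | .071 | .065 |
| .5/.45/.65 | .8/1/1.1 | .072 | .100 |
| .6/.5/.7 | .7/1/1.2 | .087 | .134 |

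So the planned test holds 5% only when variances and correlations are equal across waves. Dropping Tx from the intercept while keeping the random-intercept covariance can make the error rate worse.

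**The case against.** A difference-in-change model with a random intercept is a recognised analysis, and nothing in the documents contradicts it. The size of the loss rests on a correlation the documents do not give and on a Gaussian model the SAP may not use. The largest contrast, about 15 points at r = .3, compares the remedy with the weaker planned test. The planned model is also more robust in one respect: if students were excluded after randomization and a real baseline gap g arose and persisted, it would cancel from the difference in change but bias a baseline-adjusted estimate by (1 − r)g. All of this stands. It makes the point an improvement, caps the claimed gain at about 3 to 10 points, and makes analysis as randomized a condition of the fix.

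Three stronger readings are tempting but not supported.

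- *That chance imbalance invalidates the planned test.* Under equal variances and correlations, the test rejects a true null in 24%, 19% or 13% of trials whose baseline gap reaches p<.05, but in 4.0%, 4.3% or 4.6% of the others. Overall, for r = .3, .05 × .24 + .95 × .040 = .050.
- *That the covariate rule fails to correct imbalance.* A baseline covariate entered only as a main effect would leave the Tx-by-time estimate unchanged with complete Gaussian data. But the SAP does not say how covariates enter, so only the missing detail is established.
- *That the SAP's power statement is wrong.* It defines neither d nor the correlation, so these figures cannot refute it.

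**Conclusion.** The point holds as a cheap improvement. The model does not use the equality of the arms at a baseline taken before randomization, and so loses precision. The free baseline term introduces no bias; a 5% error rate needs the further assumption of equal variances and correlations across waves.

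The benefit matters at the small effect the SAP targets and is at most about 2.5 points at d=.40 with 300 per arm. It rests on the assumed r, the Gaussian form and the assumed dropout pattern. Under a Poisson model it may be negligible or large, and no gain was computed for baseline adjustment of follow-up counts.

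**What to change.** Specify one of the following in the SAP.

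- **(a) Gaussian model only.** Drop Tx from the intercept equation and require an unstructured within-student covariance or robust standard errors. The second condition is not optional, given the error rates above. The Tx-by-time term is then also the per-visit difference.
- **(b) Gaussian or count model.** Model the 1- and 6-month outcomes with Tx, time and Tx-by-time, adjusting for the baseline value of the same outcome by time, for example log(baseline + 1) for counts.

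Use this pre-specified adjustment, plus birth sex as the balancing factor, in place of the imbalance-triggered covariate rule. Report baseline comparisons descriptively.

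State that every student with a randomized parent is analysed as randomized. Protocol section 3 places account creation after randomization ("Parents who click the link will be prompted to create their user account"), so dropping families who never sign up would undermine the common baseline. The statement should also say how Tx is set when two parents take part, which Protocol section 5 allows: "If more than one parent decides to participate their PINs will end in either -1 or -2".

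The cost is SAP wording and no new data. The downsides are a few more covariance parameters under (a), a simple rule for skipped baseline items under (b) (students may skip questions, Protocol section 4), and reliance on analysis as randomized.

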2. SUBJECT RECRUITMENT

How will subjects be selected? What is the sex and age range of the subjects? Approximately how many subjects will be studied?

How will subjects be contacted? Who will make initial contact with subjects? Specifically, what will subjects be told in initial contact?

If subjects will be screened, describe criteria and procedures.

This study seeks to evaluate both feasibility and efficacy of the FITSTART+ app-based intervention for parents. The goal is to assess efficacy of the intervention version of the FITSTART+ app on student alcohol outcomes, relative to an active control version of the app. Participants in the clinical trial will ultimately be 400 to 600 LMU students who have a parent randomized to use either the intervention or control version of the app. The Registrar will provide student and parent contact information for the incoming freshman class (approx. 1600 students and 3000 parents). Incoming traditional, non-international first-year students (i.e., first-time college students aged 17–20 years) registered to attend LMU during the Fall semester and who have at least one parent/guardian email on file with the admissions office will be emailed an invitation to participate in a three-part web-based survey assessing experiences during their first year of college. Invitations to complete the baseline survey will be sent in July 2021 (T1) via the admissions office who will verify each student's age, year in school, and whether they have a parent/guardian email on file. The baseline survey and each follow-up survey will be open for

approximately 3 weeks. Student participants will receive a \$25 electronic gift card for completing each study survey and an additional \$10 bonus if they complete all three surveys.

To participate in the study, students must:

- 1) Be a first-year college student 17–20 years of age.
- 2) Have a parent/guardian email on file with the admissions office.
- 3) Be a domestic (i.e., non-international) student.
- 4) Consent to participate (with parental consent for minors under age 18).

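### The SAP handles within-student correlation with a random intercept alone, so in the Gaussian version the standard errors of the 1-month and 6-month effects can be wrong in either direction

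*SAP*

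**What the plan says.** The SAP's two-level model has an intercept and two time dummies per student, each regressed on treatment. Only the intercept equation has a student-level residual (r00i); the equations for the two time effects have none. The text assigns the whole job of handling correlation to that term: "The intercept includes a random effect, which will model the subject-specific heterogeneity in the outcome and control for correlated data due to individuals".

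Treatment also enters the intercept equation, so that "intercept treatment differences will represent treatment differences at baseline". The effects of interest are therefore beta11 (change to 1 month) and beta21 (change to 6 months, from the dummy defined as "T2 = student baseline [coded 0] to 6 months into college follow-up [coded 1"). The Protocol, section 2, places baseline before college: "Invitations to complete the baseline survey will be sent in July 2021 (T1". (The Protocol uses T1 for baseline, whereas the SAP uses T1 for the 1-month dummy.)

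Two further statements limit the reach of the point. Under Additional Model Considerations the error distribution is left open: the team will consider whether the "Level 1 components are more appropriately modeled as Gaussian or Poisson". The SAP also lists a second comparison: "Pairwise comparisons (post hoc Tukey's) were conducted to examine mean differences between conditions at each time point".

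Neither document states a residual covariance structure, a robust standard error, an alpha level, a correlation between waves or an SD by wave.

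**The concern.** With Gaussian errors that are independent given a random intercept, all three waves share one variance and every pair of waves shares one correlation. The waves here are unequally spaced and span the move to college. The baseline-to-6-month correlation is the natural candidate for the lowest of the three, and drinking may vary more or less between students after they arrive. The model nevertheless uses one pooled residual variance for both change contrasts. If the true change variances differ, at least one contrast gets the wrong standard error, and with it the wrong confidence interval and p-value. The 6-month contrast is the trial's longest-term efficacy result.

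A second, separate matter is precision. Because beta01 is free, beta21 is a plain difference in changes and makes no use of the fact that randomization equalizes the arms at baseline. The SAP says it aims at small effects (d = 0.20), where lost precision matters.

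**Working it through.** **Plan's own figure.** There is none to reproduce: the SAP states no type I error or standard error, and its power statement gives no number.

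**Inputs.** From the SAP: random intercept only; three waves; 300 per arm with 20% attrition in the power curves, so 300 x 0.80 = 240 per arm; d = 0.20. Assumed: two-sided 0.05, complete data, and the correlations and SDs in the table.

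**Formula.** Let V01, V06 and V16 be the true variances of the change from baseline to 1 month, baseline to 6 months, and 1 to 6 months. Each is the sum of the two wave variances minus twice the correlation times both SDs. The random-intercept model replaces each of them by their mean, M. At 6 months the ratio of true to model variance is R = V06/M, and type I error = 2[1 - Phi(1.96/sqrt(R))]. At 1 month R = V01/M.

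**Worked case.** Correlations 0.6 / 0.4 / 0.6 (baseline-1, baseline-6, 1-6), equal SDs of 1: V01 = 2(1 - 0.6) = 0.8, V06 = 2(1 - 0.4) = 1.2, V16 = 0.8, M = 2.8/3 = 0.933. At 6 months sqrt(1.2/0.933) = 1.134, giving 8.4%. At 1 month sqrt(0.8/0.933) = 0.926, giving 3.4%. A simulation of 20,000 trials with 240 per arm gave 8.4% and 3.3%; using the 6-month change's own variance gave 5.1%.

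| Correlations | SDs (baseline, 1, 6 months) | V01, V06, V16 | M | 6-month type I | 1-month type I |
|---|---|---|---|---|---|
| 0.7/0.65/0.7 | 1, 1, 1 | 0.60, 0.70, 0.60 | 0.633 | 6.2% | 4.4% |
| 0.6/0.5/0.6 | 1, 1, 1 | 0.80, 1.00, 0.80 | 0.867 | 6.8% | 4.1% |
| 0.6/0.5/0.7 | 1, 1, 1 | 0.80, 1.00, 0.60 | 0.800 | 8.0% | 5.0% |
| 0.7/0.4/0.6 | 1, 1, 1 | 0.60, 1.20, 0.80 | 0.867 | 9.6% | 1.8% |
| 0.7/0.4/0.7 | 1, 1, 1 | 0.60, 1.20, 0.60 | 0.800 | 11.0% | 2.4% |
| 0.7/0.5/0.7 | 1, 1, 1.3 | 0.60, 1.39, 0.87 | 0.953 | 10.5% | 1.3% |
| 0.6/0.5/0.6 | 1, 1.2, 1 | 1.00, 1.00, 1.00 | 1.000 | 5.0% | 5.0% |
| 0.6/0.5/0.6 | 0.8, 1.2, 1 | 0.928, 0.84, 1.00 | 0.923 | 4.0% | 5.1% |
| 0.6/0.5/0.6 | 0.7, 1.2, 1 | 0.922, 0.79, 1.00 | 0.904 | 3.6% | 5.2% |

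Over all eight corner combinations of 0.6-0.7 / 0.4-0.5 / 0.6-0.7 with equal SDs, the 6-month error runs from 6.8% to 11.0% and the 1-month error from 1.8% to 5.0%. The weaker decay in the first row gives the 6% end.

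**Between-arm comparison at 6 months.** Here the model uses the average of the three wave variances. With equal SDs the average is correct whatever the correlations, so the error stays at 5.0%. If the baseline SD is 0.8 of the follow-up SD, R = 1/[(0.64 + 1 + 1)/3] = 1.136, giving 6.6%. If it is 0.5, R = 1/[(0.25 + 1 + 1)/3] = 1.333, giving 9.0%.

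**Shared baseline mean.** With equal SDs and baseline-to-6-month correlation rho, the variance of the 6-month effect is proportional to 2(1 - rho) with a free baseline difference and to 1 - rho^2 with a shared mean. The ratio is (1 + rho)/2: 0.70 at rho 0.4, 0.75 at 0.5 and 0.80 at 0.6. Power at d = 0.20 with 240 per arm:
- rho 0.4: the SE falls from sqrt(2 x 1.2/240) = 0.100 to sqrt(2 x 0.84/240) = 0.0837, and power rises from 0.52 to 0.67.
- rho 0.6: the SE falls from sqrt(2 x 0.8/240) = 0.0816 to sqrt(2 x 0.64/240) = 0.0730, and power rises from 0.69 to 0.78.

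**The case against.** A reader might infer that the plan's 6-month standard error is too small, with a true error rate of 6% to 11%. The documents do not support that. They give no correlations, SDs or alpha, and the direction is not fixed. When the SD peaks just after arrival at college, the same decaying correlations give 3.6% to 5.0%. This objection stands in full. It has a limit: lowering only the baseline SD shrinks the inflation without reversing it in the case checked (0.6/0.5/0.6 with SDs 0.5, 1, 1 still gives 5.3%).

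Nor is the 1-month test always conservative: 0.6/0.5/0.7 with equal SDs gives 5.0%.

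A reader might also extend the range to every planned test. The Tukey comparison at 6 months is untouched by correlation decay when SDs are equal; it is sensitive to unequal SDs instead. A Poisson model with a log link does not force equal correlation on the observed counts, so the Gaussian range does not describe it. Choosing Poisson is not a clear escape, however. Small simulations (120 runs per case, error about 2 to 4 points) gave about 3% when one shared intercept was true and about 15% to 32% when students' underlying rates varied between waves.

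Finally, a free beta01 might be read as a mistake. It is a valid and common parameterization, introduces no bias and does not inflate type I error. The SAP's plan to test baseline equivalence and adjust for variables associated with assignment is reasonable, although it does not reliably recover the lost precision.

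**Conclusion.** The gap is real: one random intercept carries all the within-student correlation, and nothing in the SAP protects the standard errors if that structure is wrong. The consequence is conditional. For the Gaussian change contrasts with equal SDs and decaying correlation, type I error is about 6% to 11% at 6 months and usually about 2% to 5% at 1 month. With SDs that differ by wave, the 6-month figure can fall to about 4% to 5% or stay high. All these figures assume two-sided 0.05, complete data and the correlations shown.

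The baseline constraint is an optional improvement in precision, worth a 20% to 30% cut in variance at rho 0.6 to 0.4 with equal SDs. The point merits a change to the SAP because the uncertainty can be removed at almost no cost, whichever way the true covariance falls.

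**What to change.** For the Gaussian version, prespecify an unstructured 3 x 3 covariance across the waves in place of the random intercept. For a count version, keep the subject effect and base inference for beta11 and beta21 on empirical (sandwich) standard errors; the sandwich was not tested by calculation here, so a short simulation before the SAP is finalized would be sensible.

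Separately, for efficiency, remove Tx from the pi0 equation so that both arms share one baseline mean, and read the effects from beta11 and beta21. Baseline differences between arms can still be reported through the equivalence tests already planned under Additional Model Considerations. The baseline value of the outcome should then not also be added as a covariate, because it is already one of the modelled responses.

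The cost is SAP wording and a few lines of SAS. Three waves need six covariance parameters (three variances and three covariances), which the 400 to 600 students in Protocol section 2 support easily. No new data or participants are needed.
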